12.2.3 Expected Primary Efficacy Endpoint Event Rate

Occurrence of the components of the primary hierarchical composite efficacy endpoint was estimated based on published literature and special consideration of data from the DEFLECT III randomized controlled trial of the TriGuard device:

For Tier 1 of the hierarchy, an expected event rate of all-cause mortality or stroke (disabling and non-disabling) at 30 days was estimated based on published data from randomized controlled trials of subjects undergoing unprotected TAVI (Table 11).

Table 11. Composite of all-cause mortality and any stroke (30 days) in unprotected TAVI RCTs

Trial	N	Composite		Component					
		Death + All Stroke	Death + Disabling Stroke	Death	All Stroke	All stroke or TIA	Disabling / Major Stroke	Non-disabling / Minor Stroke	TIA
PARTNER 1A (High Risk)^{4*}	348	7.8% (27)	6.9% (24)	3.4% (12)	4.6% (16)	5.5% (19)	3.8% (13)	0.9% (3)	0.9% (3)
PARTNER 1B (Inoperable)⁵	179	10.1% (18)	8.4% (15)	5.0% (9)	6.7% (12)	6.7% (12)	5.0% (9)	1.7% (3)	0% (0)

CoreValve High Risk^{6*}	390	6.9% (27)	5.9% (23)	3.3% (13)	4.9% (19)	5.9% (23)	3.9% (15)	1.0% (4)	0.8% (3)
CoreValve Extreme Risk^{7*}	489	11.5% (56)	9.8% (48)	8.4% (41)	4.0% (19)	4.5% (22)	2.3% (11)	1.9% (9)	0.6% (3)
Simple average	9.1%								
Weighted average	9.1%								
Meta-analytic average	8.8%								
NOTE: Italics indicates that the event rate is not directly reported, but the given percentage represents a best estimate based on component event rates; for the composite of death and all stroke, it is assumed that no subject with a non-disabling stroke also experienced a death or disabling stroke within the 30-day timeframe (with the exception of CoreValve Extreme, in which data indicates that 1 subject experienced both a major and a minor stroke).									
*Percentages given are Kaplan Meier estimates, and therefore do not equal the number of subjects experiencing an event divided by the total number of subjects									

In addition, we took into account randomized control trials of subjects randomized to TAVI with vs. without protection device (table 11a).

Table 11a. Rates of death and Stroke at 30 days in RCTs of protection devices.

Trial*	N	Death at 30 days		Stroke at 30 days	
		Device	Control	Device	Control
DEFLECT III ⁸ 2015	85	2.17%	5.13%	4.35%	5.13%
EMBOL-X ⁷² 2015	30	0%	0%	--	--
MISTRAL-C ⁷³ 2016	65	3.12%	9.09%	0%	6.06%
CLEAN TAVI ⁷⁴ 2016	100	0%	2%	8%	8%
SENTINEL ⁹ 2017	363	1.28%	1.8%	5.63%	9.09%
Simple mean		1.32%	3.6%	3.6%	5.66%
Weighted mean		1.33%	3.21%	5.09%	7.25%
Meta-analytic mean*		1.6%	3.83%	5.09%	7.26%

* Embol-X excluded

A recently published letter¹⁰⁴ presented a meta-analysis of the above trials for the primary end point of death and stroke at longest follow-up available, showed rates of 6% vs 10% for device vs. control respectively.

Based on the above, and considering SENTINEL being the most recent trial (with up to 9% stroke rate and 1.8% death rate in the controls), we conservatively estimate an ~11% rate of all-cause mortality or stroke at 30 days in subjects undergoing unprotected TAVI and a 50% reduction yielding a ~6% assumed event rate in the protected group.

The remaining component event rates (Tiers 2-4) are estimated based on data from the above mentioned trials, which employed identical NIHSS assessments and DW-MRI analysis methodology.

We conservatively expect 9% of controls and 6% of device group patients to have any NIHSS worsening ([table 6b](#)).

Among subjects who survived free of stroke to 30 days, and who did not experience NIHSS worsening at the post-procedure (2-5 days post-procedure) assessment (Tier 3 of the hierarchy), we expect 11% of controls and 27% of device group patients to be free of any lesions on MRI. These assumptions are based on the above trials and more specifically on the published results of DEFLECT III⁸ (Per Treatment) which used a similar device with full cerebral protection (as opposed to SENTINEL) and the same MRI assessment modality as planned in this trial (see also [table 6a](#)).

Among patients surviving without stroke at 30 days, and who did not experience NIHSS worsening, and who had MRI lesions on DW-MRI (final 4th Tier) we expect the rates of lesion volumes categorized by size in pre-specified set ranges of >0-50 mm³, >50-150 mm³ and above 150 mm³ to be 7%, 33%, and 48% in the controls, respectively, and 19%, 7.5% and 46% in the device arm, respectively. Expected rates were adapted from DEFLECT III (Per Treatment), the only published study thus far to incorporate such volume subdivisions.⁸

All tiers and their respective assumed rates are presented in [table 11b](#).

Table 11b. Assumed event rates

	Assumed Control Rates	Assumed TriGUARD 3 Rates
Death or Stroke	11%	6%
Worsening NIHSS	9%	6%
Freedom from MRI Findings (Lesion Volume 0 mm³)	11%	27%
Lesion Volume (mm³)		
>0-50	7%	19%
>50-150	33%	7.5%
> 150	48%	46%

15% Missing in MRI Follow-up and 5% missing for all other parameters

Type I Error = 5%

The primary analysis population for the primary endpoint is the efficacy Intention to Treat (eITT) population (§12.3.1), which excludes subjects with conversion to surgery or prolonged cardiac arrest prior to the post-procedure DW-MRI. Selection of this population as the primary analysis population for the efficacy endpoint ensures that, should a small number of subjects experience an adverse endpoint event due to circumstances unrelated to procedural neuroprotection, the study will remain powered to detect a clinically-meaningful treatment effect, particularly regarding the volume of subclinical cerebral ischemic lesions on DW-MRI.

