Given these assumptions, the initial randomized cohort sample size of 225 subjects (2:1 randomization with 150 Intervention and 75 new control patients) will provide a power of >80% to demonstrate superiority (1-sided $\alpha=0.025$) of the intervention group over the control group for the primary efficacy endpoint. Notably, in several simulations, considering different distributions for lesion volume and different distributions for death/ stroke, the study power remained greater than 80%. Adding the 63 control subjects already enrolled in REFLECT phase I for a total of 138 control subjects would increase the power to at least 92% to demonstrate superiority of the primary efficacy endpoint; poolability of the Phase I and Phase II control subjects will be assessed at the time of the primary analysis and the results will determine the control population used for the primary analysis of the primary efficacy endpoint. 5% loss to clinical follow up at 30 days is included.

As a primary efficacy analysis, the primary efficacy endpoint will be evaluated in the efficacy Intention to Treat (eITT) population. The eITT population is defined as:

- Subjects who are enrolled in the trial and randomized to a treatment group, regardless of treatment actually received AND
- Who do not have conversion to surgery or prolonged cardiac arrest (>3 minutes) prior to the post-procedure DW-MRI

Selection of the eITT population as the primary analysis population for the primary efficacy endpoint ensures that, should a small number of subjects experience an adverse event due to circumstances unrelated to procedural neuroprotection (i.e., conversion to surgery or prolonged cardiac arrest prior to the post-procedure DW-MRI), the study will remain powered to detect a clinically-meaningful treatment effect, particularly regarding the volume of subclinical cerebral ischemic lesions on DW-MRI.

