4.1.5 Prevention of Periprocedural Cerebral Embolism

The devastating consequences of periprocedural stroke during TAVI, as well as concern regarding potential long-term neurocognitive sequelae of subclinical cerebral embolic events, have prompted investigation into methods to minimize or prevent periprocedural cerebral embolism during cardiac surgery and endovascular interventions. Because atheromatous and calcific embolic are substantial contributors to cerebral embolism during TAVI, a mechanical means of preventing such material from reaching the cerebral circulation could be an effective approach. Because approximately 50% of TAVI-related neurological events are directly procedure-related,²³ such devices could have a meaningful impact on stroke and other cerebral embolic events in TAVI patients.

The DEFLECT I Trial (NCT01448421) of the first-generation TriGuard cerebral embolic protection device (CEPD) (from which the TriGuard HDH device and the TriGUARD 3 device used in the present study were developed) demonstrated good procedural success and safety, as well as a reduction in total per-patient cerebral ischemic lesion volume after TAVI with embolic protection compared with a historical control of unprotected TAVI.⁷⁵

Table 6. Comparison of Post-TAVI DW-MRI Lesion Data for TAVI Without vs. With Embolic Protection

Parameter	Unprotected TAVI Historical Average	TAVI with Embolic Protection
Incidence of lesions [proportion of patients]	77%	78.6%
Number of lesions [mean (range)]	4.6 (0-36)	5.1±6.1 (0-28)
Single lesion volume [mean (range)]	0.33 (0.075 – 0.76)	0.13±0.13 (0 – 0.47)
Total lesion volume [mean (range)]	2.18±4.5 (1.65 – 4.3) cm ³	0.77±0.96 (0 – 3.94) cm ³
Results of the DEFLECT I trial of the first-generation TriGuard device (n=28 subjects with paired DW-MRI) compared with Historical Average (Tables 1-4 above)		

Thus far, several randomized control trials have addressed the issue of embolic protection device during TAVI.

The DEFLECT III trial⁸ included 85 patients and evaluated the efficacy of the TriGuard HDH device. Complete cerebral vessel coverage was achieved in 89% of subjects. Device use was associated with greater freedom from ischemic brain lesions and a shift towards smaller lesion volumes compared to controls. Clinically, device protection afforded better neurocognitive function and numerically lower rates of death and stroke.

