The EMBOL-X trial⁷² included 30 patients, with half of the patients randomized to protection with the EMBOL-X device (self-expandable mesh placed in the aorta). Protected patients had fewer lesions and the authors reported statistically significant smaller lesion volumes in the supply region of the MCA. No mortality was observed in this trial in both groups.

Mistral- C⁷³ included 55 patients with 1:1 randomization to protection with the SENTINEL device (2 cone shaped filters placed into the brachiocephalic trunk and the left common carotid artery). Patients with SENTINEL protection had numerically fewer lesions and a

smaller total lesion volume. Neurocognitive deterioration was present in 4% of patients with device protection and 27% of patients without ($p=0.017$). Mortality was also reduced in the device arm (not statistically significant).

CLEAN-TAVI⁷⁴ published in 2016 included 100 patients with 50 patients randomized to device protection with Claret (2 cone shaped filters described above). The trial showed a statistically significant reduction in the number of lesions and total lesion volume in the device arm. Stroke rates were similar between groups and one death occurred in the control group.

Finally, the recently published SENTINEL trial⁹ included 119 controls and 242 device patients (including 123 safety patients). Patients in the device arm had smaller lesion volumes and a lower number of lesions. Stroke rates were reduced in the device arm but no difference was noted in neurocognitive function between groups.

* MRI and other clinical results in the trials above were not statistically significant unless otherwise mentioned.

Major trials and their MRI findings are summarized in table 6a. A comparison of the different clinical endpoints assessed in these trials is presented in table 6b.

Table 6a. MRI findings in RCTs using device protection in TAVI.

Trial*	N	Percent of patients with MRI lesions		Median Number of MRI lesions		Median Total Lesion Volume (mm ³)***	
		Device	Control	Device	Control	Device	Control
DEFLECT III ⁸ 2015	85	78.8%	88.46%	7	4	100.9****	110****
EMBOL-X ⁷² 2015	30	57.14%	68.75%	1.28**	2**	--	--
MISTRAL-C ⁷³ 2016	65	72.73%	86.67%	--	--	95	197
CLEAN TAVI ⁷⁴ 2016	100	97.96%	97.78%	5	10	205	472
SENTINEL ⁹ 2017	363	--	--	3	5	294	309.8

* Based on published results where available. CLEAN-TAVI results of number of lesions and volume were statistically significant.

** Unclear calculation methodology in the paper.

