12.2.1.1.2 Primary Efficacy Hypothesis

The primary hypothesis is that TAVI with the TriGUARD 3 system is superior to standard (unprotected) TAVI for the primary hierarchical composite efficacy endpoint of all-cause mortality or any stroke at 30 days (Tier 1), NIHSS worsening from baseline assessed at 2-5 days post-procedure (Tier 2), freedom from any cerebral ischemic lesions detected by diffusion-weighted magnetic resonance imaging (DW-MRI) 2 to 5 days post-procedure (Tier 3), and total volume of post-procedure cerebral ischemic lesions detected by DW-MRI (Tier 4).

Specifically, the primary efficacy hypotheses are:

H_0 : The hierarchical composite of death/stroke, NIHSS worsening, freedom from any lesions detected by DW-MRI, and larger total lesion volumes is not different between Intervention and Control groups

H_1 : The hierarchical composite of death/stroke, NIHSS worsening, freedom from any lesions detected by DW-MRI, and larger total lesion volumes is lower in the Intervention group than in the Control group

The null hypothesis will be tested at the final analysis at a one-sided 0.025 level of significance. The null hypothesis will be tested using the chi-square test according to the method described in Finkelstein-Schoenfeld² and Pocock⁷⁷.

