12.2.4.1.2 Primary Efficacy Endpoint

Sample size for assessing superiority of Intervention over Control with respect to the hierarchical composite primary efficacy endpoint was estimated using the following assumptions:

- All-cause mortality or any stroke at 30 days will occur in ~11% of Control subjects and ~6% of Intervention subjects (5% absolute reduction, ~45% relative reduction)
- Among subjects without all-cause mortality or any stroke to 30 days, NIHSS worsening 2-5 days post-procedure will occur in 9% of Control subjects and 6% of Intervention subjects (3% absolute reduction, 33.3% relative reduction)
- Among subjects without all-cause mortality or any stroke to 30 days and without NIHSS worsening 2-5 days post-procedure, MRI findings will occur in 89% of Control subjects and in 73% of intervention subjects (16% absolute reduction, 17.9% relative reduction).
- Among subjects without all-cause mortality or any stroke to 30 days, without NIHSS worsening 2-5 days post procedure, but with MRI findings, lesion volumes can be divided into 3 out of 4 subsets- 0 mm³, >0-50 mm³, >50-150 mm³ and >150 mm³. For these volume subsets, we expect rates of 11%, 7%, 33% and 48%, respectively, in the control group and 27%, 19%, 7.5%, and 46%, respectively, in the intervention group.
- For sample size calculations a relative reduction of 30% is expected in each lesion volume subset, based on the comparison of total lesion volumes between device and control groups in DEFLECT I, MISTRAL C⁷³ SENTINEL⁹ and CLEAN-TAVI⁷⁴.
- The smallest detectable difference in MRI is a single voxel. In addition, inter-rater mean differences between two independent observers was 15% or ~5 voxels (40.5 mm³) in the KSH Methodology/Reproducibility Study (data on file). Accordingly, a meaningful difference to declare a win/lose between MRI lesion volumes was set at a 15% relative difference or a 50 mm³ absolute difference.

- Loss to post-procedure DW-MRI follow-up is expected to occur in 15% of all subjects (due to contraindications to post-procedure DW-MRI [e.g., pacemaker implantation] or subject non-compliance)
- Loss to follow-up for all other reasons is expected to be 5%.
- Overall α (one-sided)=0.025; (see §12.4.2)

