To determine the required sample size, calculations were performed by simulating 5000 samples on SAS software postulating the above parameters; mortality and stroke rates and proportions of patients with NIHSS worsening, any MRI lesions and volumes divided to subsets were simulated by a random binary function.

An evaluable sample size of 225 subjects (2:1 randomization with 150 in the Intervention group and 75 new Control subjects) is sufficient to demonstrate superiority of the Intervention group to the Control group for the primary efficacy endpoint when pair-wise comparisons are made between subjects using the Finkelstein-Schoenfeld method,² and outcomes between treatment groups are compared by the chi-square test.

Therefore, the initial randomized cohort sample size of 225 subjects (150 in the Intervention group and 75 new control subjects) will have >80% power to demonstrate superiority of the Intervention group for the primary efficacy endpoint (one sided $\alpha=0.025$). Notably, in several simulations, considering different distributions for lesion volume and different distributions for death/ stroke, the study power remained greater than 80%.

Adding the 63 control subjects already enrolled in REFLECT Phase I for a total of 138 control subjects would increase the power to at least 92% to demonstrate superiority of the primary efficacy endpoint. 5% loss to follow up is included.

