12.3 Analysis Populations

12.3.1 Efficacy Intention to Treat (eITT) Analysis Population

The efficacy Intention to Treat (eITT) analysis population is defined as:

- Subjects who are enrolled in the trial and randomized to a treatment group, regardless of treatment actually received AND
- Who do not have conversion to surgery or prolonged cardiac arrest (>3 minutes) prior to the post-procedure DW-MRI

The eITT population of evaluable (i.e., not Roll-In) subjects will be used for the primary analysis of the primary efficacy endpoint, the primary analysis of the secondary hypothesis-driven endpoints, and the primary analysis of all secondary neurologic efficacy endpoints.

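### The MRI inputs to the Phase II efficacy power are per-treatment rates, but the primary test is run in eITT and no allowance is made for incomplete coverage

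*Combined protocol and SAP*

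**What the plan says.** **Inputs.** Section 12.2.3 bases the Tier 3 rates chiefly on the per-treatment results of DEFLECT III, the earlier randomised trial of TriGuard HDH. Its reasons are a similar device with full cerebral protection and the same MRI assessment. For the Tier 4 volume classes it says "Expected rates were adapted from DEFLECT III (Per Treatment". Section 12.2.4.1.2 carries these numbers into the simulation: "MRI findings will occur in 89% of Control subjects and in 73% of intervention subjects". The classes (0, >0-50, >50-150, >150 mm³) are 11/7/33/48% in controls and 27/19/7.5/46% in the device arm.

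**Stated power.** With 150 device subjects and 75 new controls the trial "will have >80% power to demonstrate superiority". Adding the 63 Phase I controls (138 in all) is said to give at least 92%. The synopsis adds that, in several simulations "considering different distributions for lesion volume and different distributions for death/ stroke, the study power remained greater than 80" percent; section 12.2.4.1.2 says the same.

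**Analysis population.** Under section 12.3.1 the eITT population "will be used for the primary analysis of the primary efficacy endpoint". It keeps randomised subjects whatever treatment they received, and excludes only conversion to surgery or prolonged cardiac arrest before the MRI. Section 12.3.4 defines the per-treatment set as device subjects with positioning maintained and complete coverage, plus all controls. That set serves only an additional analysis.

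**Source trial.** Section 4.1.5 reports "Complete cerebral vessel coverage was achieved in 89% of subjects". Table 6a, under "Percent of patients with MRI lesions", gives 78.8% for device and 88.46% for control in that trial.

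**The concern.** The MRI rates describe subjects in whom the device worked as intended. The test will be run on everyone randomised to it. The only losses allowed for are 15% missing MRI and 5% other follow-up; nothing covers device subjects with partial, lost or no coverage.

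This matters because the MRI tiers carry most of the power. In the simulation below (75 controls, base case), removing all MRI effect leaves 18%. Replacing the per-treatment device classes with the control classes, while keeping the 30% volume reduction, gives 54%. A null eITT result would therefore be read against a power figure that has not been shown for that analysis.

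**Working it through.** **Inputs from the documents.** Death or stroke 6% v 11%; NIHSS worsening 6% v 9%; the volume classes above; a 30% relative volume reduction within each class; a Tier 4 win at a 15% relative or 50 mm³ absolute difference; 15% missing MRI and 5% other loss (section 12.2.4.1.2). The test level is set in 12.2.1.1.2: "The null hypothesis will be tested at the final analysis at a one-sided 0.025 level of significance".

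**Assumptions, because the documents are silent.** Volumes are uniform within the lower classes. Above 150 mm³ they are log-uniform up to a limit of 500, 1500 (base case) or 5000 mm³. Events fall early, NIHSS increases are 1-3 points, and subjects lost to follow-up are dropped. Classes are rescaled to sum to 100%.

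**Method.** Four-tier Finkelstein-Schoenfeld scores over all pairs, with permutation variance, rejecting at one-sided 0.025. The simulated null rejection rate was 0.025. There were 2000 runs per cell, so the Monte Carlo standard error near 77% is √(0.77 × 0.23 / 2000) ≈ 0.9 points.

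**Scenarios.**
- A: the plan's own inputs.
- B: 89% of device subjects have the per-treatment MRI rates; 11% have control MRI rates with no volume reduction. Lesion-free rate = 0.89 × 27% + 0.11 × 11% = 25.2%.
- C (more pessimistic): lesion-free rate from Table 6a, 100% − 78.8% = 21.2%. The other device classes are scaled up by 78.8/72.5 and the 30% reduction is kept.

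Power, for top-class limits of 500 / 1500 / 5000 mm³:

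| Scenario | 150:75 | 150:138 |
|---|---|---|
| A, plan's inputs | 92 / 82 / 78% | 98 / 94 / 90% |
| B, 89% coverage | 87 / 77 / 71% | 96 / 91 / 87% |
| C, 21.2% lesion-free | 84 / 71 / 63% | 95 / 86 / 80% |

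**Reading the table.** Scenario A reproduces the stated figures in the base case (more than 80%; at least 92%). From A to B with 75 controls the loss is 91.5 − 86.8 = 4.7, 82.0 − 77.0 = 5.0 and 77.8 − 71.3 = 6.5 points. With 138 controls it is 1.9, 3.1 and 3.8 points.

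A separately coded simulation gave about 80% (79-92%), 76% (71-88%) and 72% (64-82%) for A, B and C with 75 controls. Taking both together:
- B: about 76-77% (71-88%) with 75 controls and 88-91% (84-96%) with 138.
- C: about 71-72% (63-84%) with 75 controls and 85-86% (76-95%) with 138.

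**The case against.** **The choice is disclosed and the calculation is right.** Both points stand. A reader might infer an arithmetic error, but the stated figures follow from the stated inputs. Nor does the power rest wholly on per-treatment data: Tiers 1-2 and the 30% reduction are not labelled so.

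**Table 6a's 21.2% is not established as the eITT rate.** This also stands. Only the volume columns carry the per-treatment footnote, and the control figure (88.46%) agrees with the assumed 89% while the device figure does not. That suggests an all-subject result, but the table does not state its population. Its heading also shows no conditioning on freedom from death, stroke and NIHSS worsening, which the Tier 3 input has. Incomplete coverage alone does not explain the figure: even if every uncovered subject had lesions, 89% coverage gives 0.89 × 27% = 24.0%. Reaching 21.2% by mixing in control rates needs a per-treatment share of (21.2 − 11)/(27 − 11) = 64%. Scenario C is therefore a sensitivity case only.

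**The device has been redesigned.** Section 4.3.4 expects better performance from TriGUARD 3 but gives no coverage rate. Carrying over 89% is an assumption; so is the plan's implicit 100%, which is not stated.

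**The robustness statement.** A reader might infer that it is false. Its scenarios are not described, so the documents cannot show that. Nor do they say that an eITT-type dilution was included.

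**Re-estimation and pooling.** Section 12.1.1 allows an increase up to the 295-subject limit if conditional power is above 40% and below 80%, subject to sponsor approval. By normal approximation, 77% at 225 becomes Φ((0.74 + 1.96) × √(295/225) − 1.96) = Φ(1.13) ≈ 87% at a fixed 295. Pooling Phase I controls helps too, subject to a poolability assessment. Both soften the consequence; neither corrects the stated design power.

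**Conclusion.** The mismatch is explicit in the text and holds as a problem of input population. At the source trial's 89% coverage the loss is roughly 4-7 points with 75 controls, to about 76-77% (71-88%). With 138 controls power is about 88-91% (84-96%), around or a little below the stated 92%. The more pessimistic Table 6a case gives about 71-72% (63-84%) and 85-86% (76-95%).

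A reader might infer that the trial certainly lacks 80% power in eITT. The documents do not support that: they give neither the as-randomised volume classes nor the distribution above 150 mm³, and the range spans 80%. What they support is that the two power figures are not shown to apply to the eITT analysis to which they are attached. The sizes rest on HDH coverage carrying over to TriGUARD 3 and on uncovered subjects having control MRI results.

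**What to change.** In sections 12.2.3 and 12.2.4.1.2 and the synopsis, re-run the existing simulation with one of the following, and restate the eITT power for 150:75 and 150:138:
- the source trial's as-randomised MRI rates and volume classes, which are not in these documents and would have to be obtained; or
- an explicit dilution for incomplete or unmaintained coverage, with the assumed coverage rate given.

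Otherwise, label the more-than-80% and 92% figures as resting on per-treatment MRI rates, print the power under an eITT scenario beside them, and say whether the robustness simulations included such a scenario.

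The cost is one re-run and some rewording. The stated power becomes less favourable; no extra patients are needed.
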